Number of Patients: At most 2 pilot operations / study centre + Planned 13 operations required for analysis; Total 35 patients to be enrolled, appreciating the potential drop-outs.

Diagnosis and Main Criteria for Inclusion and Exclusion:

Diagnosis:

Children with an unstable midshaft (diaphyseal) forearm (radius and/or ulna) fracture.

Main inclusion and exclusion criteria: The subject and/or guardian has signed and dated the informed consent, the subject is 5 to 16 years of age, the subject has no previous fracture or infection of the study region, no metabolic bone disease, no systematic disease or medication affecting bone quality or resistance to infection.

Medical Test Device installation and identification:

The device is surgically implanted. The batch of device is identified by test device name, packaging date and clinical investigation number A2228-CIP-1.

Duration of Treatment:

The follow-up of the patients will be 104 weeks (2 years). The control device will be removed 6 months after operation. The bioabsorbable device is expected to retain its mechanical functionality for at least 8 weeks, while the complete bioabsorption of the device in human body is expected to take place within approx. 2 years.

Criteria for Evaluation:

Repeated examination of functional, clinical and radiographic outcome, and bone union formation by range of motion measurement, radiography (plain radiographs). Magnetic resonance imaging for a randomly selected subgroup of at least 10 patients treated by test device, general questionnaires.

Efficacy:

The success of fixation will be determined by radiographic measurements in comparison between the immediate postoperative state and 6, 12 and 26 weeks after surgery.

Safety:

Continuous evaluations of safety parameters and specific evaluations of adverse events and serious adverse events will take place at each postoperative study visit. The safety variables to be evaluated include adverse events, findings from physical and radiographic examinations, subjective reports of pain and functional outcome assessments.

Statistical Methods:

The primary variable will be analysed using an analysis of variance model for repeated measurements. Treatment differences with 95% confidence intervals will be calculated from the model.

Identification of the Investigational Device

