1.1.13 Safety Variables

Incidence of adverse events (AE) and serious adverse event (SAE) will be expressed as proportion per group. These consist of e.g. complications related to injury or treatment and will be separated into resolved versus long-term or non-resolved complications, which included a need for return to the operating room. Monitored AE's are:

Clinical Investigation Plan

Bioabsorbable Intramedullary Nail Fixation of Forearm Fractures in Children

- Fracture delayed union, nonunion and malunion
- Incidence of infection
- Intra-operative complications related to fixation hardware
- Need for secondary reduction due to fracture instability
- Osteolysis
- Biocompatibility reactions
- Mechanical implant failure

The potential drop-outs by any reason are recognized and reported, despite the lack of 2-year follow-up data, whilst no comparisons at end-point are available.

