1.1.14 Other Variables

Other variables documented in CRF are:

- Operation time
- Number of days lost from usual activities
 - Parents lost working days
- Length of hospitalization stay
- Complaints in daily living
- Esthetics

Statistics

Recommended statistical methods will be applied. All deviations made after approval of the CIP will be described and justified in the final study report.

Sample Size Considerations

Primary outcome variable in this study is loss of supination and pronation within 6, 12, 26, 52, and 104 weeks after surgery. The non-inferiority margin is set to be 80 % in the calculations (=Power).

It is previously known that the forearm pronation in this age group is 81.2 degrees (95% CI 79.6-82.28) and 79.6 degrees (95% CI 78.8-80.4) in girls and boys, respectively. The corresponding supination archs are 90.0 degrees (95% CI 88.0-92.0) and 87.8 degrees (95% CI 85.7-89.9). [26] The standard deviation (SD) is 6.1 degrees in pronation and 7.6 degrees in supination. We determined that the new method (ActivaNail –intramedullary fixation) should

Clinical Investigation Plan

Bioabsorbable Intramedullary Nail Fixation of Forearm Fractures in Children

result to the forearm rotational range of motion that is not more than 15 degrees lower, compared to the rotational range of motion in TEN group, according to the Price's classification (<15 degrees of decrease refers to excellent outcome).

Difference between means in the groups is set as 7.0 and the Alpha as 0.05. The sample size is estimated to be 13 experimental subjects and 13 controls according to an unpaired two sample Student t test. This study population will also be exclusively large enough to recognize decrease in the ROM that is clinically significant (>15 degrees of decrease in supination or pronation in ActivaNail compared to TEN group).

Statistical Hypothesis

The following hypothesis will be tested for the primary efficacy variable:

H₀: Investigational device is inferior to comparative devices

H₁: Investigational device is non-inferior to comparative devices

The non-inferiority limit is set to 80 %. Thus, non-inferiority is shown if the upper limit of the 95% confidence interval for the difference is less than or equal to 5 %.

Statistical Methods

All operated subjects who reach the 2-year follow-up will be included in the statistical analysis. Study data will be tabulated by treatment groups with descriptive summary statistics.

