The study data of the CRFs will be stored at the research sites and copies without personal identification data will be sent to the sponsor for storing.

Clinical Investigation Plan

Bioabsorbable Intramedullary Nail Fixation of Forearm Fractures in Children

Quality Assurance

Bioretec has a certified Quality Management System according to ISO 13485:2003. Investigational devices will be tested according to SOP's of the Bioretec Ltd using the test equipment maintained and calibrated according to relevant SOP's of Bioretec Ltd.

Discontinuation and Withdrawal of Subjects

A subject may be discontinued (withdrawn) from the study at any time if the subject or the investigator believes it is not in the best interest of the subject to continue participation in the study. Subjects withdrawn from the study will not be replaced, regardless of the reason for withdrawal. All study data provided up to the time of withdrawal will be collected and reported. This information will be recorded in the subject's source documentation and in the CRF. Subjects who discontinue their participation or are withdrawn from the trial will be asked to participate in a final study visit at 104-week follow-up visit.

Termination of the Study

The sponsor may terminate individual subject or group of subjects, or the entire investigation, at any time for any of the following reasons:

- Failure to enrol subjects
- Protocol violations
- Inaccurate or incomplete data
- Unsafe or unethical practices
- Questionable safety of the test device
- Suspected lack of efficacy of the test device
- Administrative decision.

If the investigator terminates the study prematurely, the investigator provides the ethical committee and the sponsor with a written statement describing why the study was terminated prematurely. Prompt compliance with this requirement is essential so that the sponsor may comply with its regulatory obligations.

Clinical Investigation Plan

Bioabsorbable Intramedullary Nail Fixation of Forearm Fractures in Children

CIP Amendments and Deviations

All amendments to the CIP with the justifications will be agreed and recorded between sponsor and the principal investigator. Any deviation to this clinical investigation plan made by investigators shall be recorded with an explanation for deviation and reported to sponsor. The significance of deviation will be determined by sponsor. When appropriate, Ethical Committee and other appropriate regulatory bodies are informed.

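### Section 14 lets the sponsor end a single test-arm child's participation for suspected failure of its own device, and the completer-only analysis can then leave that child out of the primary comparison

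*Protocol*

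**What the plan says.** Section 14 (Termination of the Study) opens: "The sponsor may terminate individual subject or group of subjects, or the entire investigation, at any time for any of the following reasons". Among the reasons are "Questionable safety of the test device" and "Suspected lack of efficacy of the test device". The list does not separate reasons for ending one subject's participation from reasons for stopping the study, and it has no corresponding entry for the titanium nail. A written explanation is required only when the investigator stops the study early.

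Section 13 (Discontinuation and Withdrawal of Subjects) opens with decisions by the subject or the investigator. It keeps and reports data up to withdrawal, and adds: "Subjects withdrawn from the study will not be replaced, regardless of the reason for withdrawal". On follow-up: "Subjects who discontinue their participation or are withdrawn from the trial will be asked to participate in a final study visit", namely the week-104 visit. Section 14 does not refer to Section 13.

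Section 10.3 (Statistical Methods) defines who is analysed: "All operated subjects who reach the 2-year follow-up will be included in the statistical analysis". The Safety Variables section says of the others: "The potential drop-outs by any reason are recognized and reported, despite the lack of 2-year follow-up data", and adds that they have no comparison at the end-point.

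The trial is unblinded (Section 9.1), the sponsor makes the test nail (Section 5), and it receives copies of the case report forms (Data Management; Report Forms). On exposure, the Synopsis says "the complete bioabsorption of the device in human body is expected to take place within approx. 2 years".

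**The concern.** Suspected lack of efficacy or questionable safety of a device are ordinary reasons for stopping a study. Applied to one child they become outcome-dependent reasons for ending observation. They can operate at subject level in one arm only, and the decision lies with a party that knows the allocation, sees the data and has an interest in the result. A non-inferiority comparison is vulnerable to this, because losing poor results from the test arm moves the estimate towards the conclusion that the trial hopes to reach.

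There is also a safety side. The nail remains in the body after participation ends, so ending participation stops observation but not exposure. If the reason was a suspected safety problem, the interim contacts are lost in the very child in whom they matter most.

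**Working it through.** **1. How a child leaves the comparison.** Three provisions have to act together:

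- Section 14 permits ending one test-arm child's participation for a test-device reason.
- Section 13 only invites withdrawn subjects to week 104, and whether sponsor terminations count as withdrawals is not stated.
- Section 10.3 analyses only those who reach two years.

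A child who passes through the first two and is not seen at week 104 falls outside the third. A child who attends week 104 could still be analysed.

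**2. Which contacts are at risk.** Table 2 collects adverse events at every contact. For a child ended at week 12, the contacts still due are the week-26 visit, the week-52 call and the week-104 visit. Section 13, if it applies, covers only the last. Weeks 26 and 52 are not secured under any reading.

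**3. The plan's own sample size.** Section 10.1 gives a difference of 7.0 degrees and alpha 0.05. With the pronation SD of 6.1, a two-sided test and 80% power, the two-sample t test needs 12.96, so 13 per group. The stated 13 is reproduced. One child is thus 1/13 of an arm of the planned minimum size.

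**4. Effect of losing one failure.** Assumed values, not in the protocol: 13 test-arm children, 12 with a mean rotation loss of 5 degrees and one losing L degrees. The shift is (12 × 5 + L)/13 − 5.

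| L | Mean with the child | Mean without | Shift | Shift / 7.0 | Shift / 15 |
|---|---|---|---|---|---|
| 20 | 80/13 = 6.15 | 5 | 1.15 | 16% | 8% |
| 30 | 90/13 = 6.92 | 5 | 1.92 | 27% | 13% |
| 45 | 105/13 = 8.08 | 5 | 3.08 | 44% | 21% |

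The 7.0 is the sample-size difference, and 15 degrees is the largest acceptable deficit in Section 10.1. With the control arm unchanged, the treatment difference moves by the same amount.

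**5. Effect on the error rate, worst case.** A simulation of 40,000 runs assumed normal data, a true deficit of exactly 15 degrees, and success if the upper 95% limit is below 15. The worst k test-arm children are removed and none attends week 104. The rule in degrees is an assumption, because Section 10.2 states its limit in per cent. Entries are the rate of falsely concluding non-inferiority.

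| Per arm | SD | k = 0 | k = 1 | k = 2 | k = 3 |
|---|---|---|---|---|---|
| 13 | 6.1 | 0.025 | 0.058 | 0.104 | 0.157 |
| 13 | 7.6 | 0.025 | 0.059 | 0.103 | 0.159 |
| 17 | 6.1 | 0.025 | 0.054 | 0.093 | 0.147 |
| 17 | 7.6 | 0.025 | 0.057 | 0.097 | 0.150 |

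Seventeen per arm is roughly the enrolment target of 35 divided by two. These are illustrations of sensitivity, not predictions.

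**The case against.** The strongest reply is that the section is headed as termination of the study, that the two reasons concern the device and not one child's poor result, and that the sponsor most likely had study-level stopping in mind. Stopping the whole study would affect both arms. That is fair as to intent. It does not change what the lead-in permits, since every reason is attached to an individual subject as well.

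The second reply is that the bias belongs to the completer rule in Section 10.3 and not to Section 14. This stands in part: without that rule a terminated child's earlier visits could still contribute. Both provisions therefore need changing.

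The third is that Section 13's wording on withdrawal is general and can be read to cover sponsor terminations, so week 104 is not lost. That reading is reasonable but unstated, and it leaves the interim contacts open.

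The fourth is that the size rests on assumed values, and that the simulation assumes selective removal of the worst results. Both are true. Measured against 15 degrees instead of 7.0, one loss in the illustration is worth 8 to 21%.

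A reader might also infer that ending participation deletes adverse events already recorded. The protocol does not support this. Section 13 keeps and reports data up to withdrawal, and drop-outs are to be reported. Only later, unobserved events can be missed.

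**Conclusion.** The concern holds as a wording defect with a real route to bias. Section 14 permits subject-level termination on grounds that exist for one arm only, and Section 10.3 turns such a termination into exclusion when the child is not seen at week 104. On the assumed values, one lost failure lowers the test-arm mean by 1.2 to 3.1 degrees. If the worst one to three results were lost, the simulated false non-inferiority rate would rise from 0.025 to about 0.06, 0.10 and 0.16 with 13 per arm. For safety, the firm statement is that the interim contacts after termination are not secured and that cover at week 104 is unclear.

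A reader might go further and infer that the plan removes test-arm failures automatically, that implanted children lose all follow-up, or that misuse is intended. The documents support none of these. Termination is discretionary, Section 13 at least arguably invites withdrawn children to the final visit, and nothing points to intent. The missing statistical analysis plan could refine the analysis set, but it would not limit the sponsor's power to end participation.

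**What to change.** 1. In Section 14, separate subject-level from study-level reasons. Confine the two test-device reasons, safety and efficacy, to stopping enrolment or the investigation. The other listed reasons are not specific to one arm. Where they are used for a single subject, items 2 and 3 limit the harm.
2. State in Section 14 that Section 13 applies to sponsor terminations. Add that every operated child whose participation is ended by the sponsor or the investigator is still offered the remaining Table 2 follow-up contacts to week 104, unless consent is withdrawn.
3. Amend Section 10.3 so that all randomised and operated subjects, pilot patients excepted, are analysed in their randomised group with all available visits, whatever the reason for termination. The planned repeated-measurements model would need to be specified in a form that accepts incomplete series.

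The cost is protocol wording, some loss of sponsor discretion over single subjects, and the completion of visits that were already scheduled. The change concerns observation and analysis only and alters no treatment.
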